2.1.3. Secondary Immunogenicity Objectives

[figure not shown]
- To describe the functional antibody responses as measured by opsonophagocytic activity (OPA) to the 13 pneumococcal serotypes induced by 13vPnC in infants and children 7 months to <6 years of age (Cohorts 2, 3, and 4) compared to responses in infants 6 weeks to 2 months of age (Cohort 1).
- To describe the immune responses to 13vPnC compared to *Haemophilus influenzae* type b (Hib)-vaccinated controls in Cohorts 2, 3, and 4.
- To describe the circulating antibody levels to the 13 pneumococcal serotypes from before vaccination through 5 years of age (4 years after the last study vaccination) in Cohort 1.

2.1.4. Secondary Safety Objective

• To evaluate the safety profile of 13vPnC as measured by the incidence rates of AEs in Cohort 1.

2.2. Study Design

- This is a phase 3 randomized, open-label study to evaluate the safety, tolerability, and immunogenicity of 13vPnC in infants and young children who are naïve to pneumococcal vaccination.
- Subjects will be stratified into 4 cohorts defined by their age pleat consent:
 - Cohort 1: Subjects 6 weeks (42 days) to 2 months (56 days) of age;
 - Cohort 2: Subjects 7 months (210 days) to <12 months (<365 days) of age;
 - Cohort 3: Subjects ≥ 1 year to ≤ 2 years of age;
 - Cohort 4: Subjects ≥ 2 years to <6 years of age.

- Subjects in Cohort 1 will all receive 13vPnC at 2, 4, 6 and 12 to 15 months of age. See Table 2 below.
- Subjects in Cohorts 2, 3, and 4 will be randomized into 2 groups in a 2:1 ratio to receive 13vPnC or comparator (Hib vaccine) according to age-appropriate schedules. See Table 2 below.

		Age at first vaccination	Age at second vaccination	Age at third vaccination	Age at fourth vaccination
Cohort 1	13vPnC	42 to 56 Days of	42 to 70 Days After	42 to 70 Days	365 to 455
		Age	Visit 1	After Visit 2	Days of Age
Cohort 2	13vPnC or	7 to <12 Months	At Least 28 Days	365 Days to <450 Days	
	Hib	of Age	After Visit 1	of Age and at Least 56	
		_		Days After Visit 2 ^a	
Cohort 3	13vPnC or	≥ 1 to <2 Years	At Least 56 Days		
	Hib	of Age	After Visit 1 ^b		
Cohort 4	13vPnC or	≥ 2 to <6 Years			
	Hib	of Age			

Table 2. Age at Vaccination

a. Subjects in Cohort 2 randomized to Hib vaccine will not receive a vaccination at Visit 3. These subjects may receive a third dose of Hib vaccine according to local practice or national recommendations, at the discretion of the investigator.

b. Subjects in Cohort 3 randomized to Hib vaccine will not receive a vaccination at Visit 2.

3. ENDPOINTS AND BASELINE VARIABLES: DEFINITIONS AND CONVENTIONS

3.1. Primary Endpoint(s)

3.1.1. Primary Immunogenicity Endpoint

• The serotype-specific immunoglobulin G (IgG) geometric mean concentrations (GMCs) for each of the pneumococcal serotypes measured 1 month after the last dose of 13vPnC in Cohort 2, 3, 4 compared to IgG GMCs measured 1 month after the infant series in Cohort 1.

3.1.2. Primary Safety Endpoints

- The incidence of local reactions and systemic events (including the use of antipyretic medication) in the 7 days after each vaccination (13vPnC or Hib) in Cohorts 2, 3 and 4.
- The incidence of AEs from the signing of the informed consent document (ICD) to 1 month after the last vaccination (13vPnC or Hib) in Cohort 2, 3 and 4.
- The incidence of newly diagnosed chronic medical conditions from 1 month after the last study vaccination (13vPnC or Hib) to 6 months after the last study vaccination in Cohort 2, 3 and 4.

PFIZER CONFIDENTIAL Page 8

[figure not shown]
• The incidence of serious adverse events (SAEs) from the signing of the ICD to 6 months after the last study vaccination (13vPnC or Hib) in Cohort 2, 3 and 4.

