8.1.4. Time Period for Collecting AE/SAE Information

The time period for actively eliciting and collecting AEs and SAEs ("active collection period") for subjects in Cohort 1, begins from the time the subject's /parent(s)/legal guardian provides informed consent, which is obtained before the subject's participation in the study (ie, before undergoing any study-related procedure and/or receiving investigational product), through and including Visit 4 and from Visit 5 to Visit 6. Between Visits 4 and 5 and between Visits 6 and 7, only SAEs and newly diagnosed chronic medical conditions will be

recorded. The subject's parent/legal guardian will be asked to report any AEs that occur within 48 hours after the blood draw at Visits 8, 9, 10, and 11.

The time period for actively eliciting and collecting AEs and SAEs ("active collection period") for subjects in Cohort 2, 3, and 4, begins from the time the subject's /parent(s)/legal guardian provides informed consent, which is obtained before the subject's participation in the study (ie, before undergoing any study-related procedure and/or receiving investigational product) until 1 month after the last vaccination (13vPnC or Hib). At the 6-Month follow-up telephone contact (final telephone contact), the parent(s)/legal guardian will be contacted to inquire about SAEs, including hospitalizations and newly diagnosed chronic medical conditions since the previous visit.

For subjects who are screen failures, the active collection period ends when screen failure status is determined.

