3.4. Safety Endpoints

3.4.1. Adverse Events

CCI

Tier-1 events: These are pre-specified events of clinical importance and are maintained in a list in the product's Safety Review Plan.

Tier-2 events: These are events that are not tier-1 but are "common". A Medical Dictionary for Regulatory Activities (MedDRA) preferred term (PT) is defined as a tier-2 event if there are at least 5% in any vaccine group.

CCL

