5. GENERAL METHODOLOGY AND CONVENTIONS

5.1. Hypotheses and Decision Rules

No formal statistical hypothesis test will be performed as this is a descriptive study and no formal hypotheses were predetermined. There are also no formal statistical decision rules for this study and a descriptive estimation approach will be used to assess all study objectives regarding safety and immunogenicity in the study.

Point estimates and nominal 95% confidence intervals (CIs) will be provided for all safety and immunogenicity endpoints at each planned analysis.

No formal multiplicity adjustments will be applied due to multiple endpoints or multiple looks of the same endpoint.

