5.2.1. Analyses for Binary Data

For immunogenicity results, the exact 2-sided 95% CIs (Clopper-Pearson CIs) will be provided for the proportions of subjects achieving an IgG concentration $\geq 0.35 \ \mu g/mL$, and the proportion of subjects with pneumococcal OPA titer \geq LLOQ for each vaccine group at defined sampling time point in each cohort, as defined in Section 3.2.1.

The exact CIs (Clopper-Pearson) for the various proportions of individual groups will be computed using the F distribution. If r is the number of responses and n is the number of subjects, then it follows that p=r/n is the estimate of the proportion of responses. An exact 95% CI can be computed by solving the following 2 equations. For the lower limit P_L ,

$$p_L = \frac{rF_L}{(rF_L + (n-r+1))}$$

and for the upper limit P_U ,

$$p_U = \frac{(r+1)F_U}{(n-r) + (r+1)F_U}$$

where F_L is the quantile from the F distribution for α =0.025, with numerator degrees of freedom equal to 2r and denominator degrees of freedom equal to 2(n–r+1). F_U is the quantile from the F distribution for α =0.975, with numerator degrees of freedom equal to 2(r+1) and denominator degrees of freedom equal to 2(n–r). When r equals 0, F_L should be set equal to 1.0 so P_L equals 0. When r equals n, F_U should be set equal to 1.0 so P_U equals 1.0.

The CI using the F distribution is described in Collett (1991) and implemented in SAS PROC FREQ.

The proportion differences for each serotype in 13vPnC between 1 month after the last vaccination of each cohort (Cohort 2, Cohort 3, Cohort 4) and 1 month after last vaccination of infant series of Cohort 1; and proportion differences between 13vPnC and Hib vaccine in Cohort 2, Cohort 3, Cohort 4 will be provided along with associated exact 2-sided 95% CIs by Chan and Zhang's method (1999).

Similarly, for the safety results in infants and children 7 months to <6 years of age (Cohorts 2, 3, and 4), the exact 2-sided 95% CIs will be provided by vaccine group in each Cohort for all primary safety endpoints, proportions of subjects reporting local reactions, systemic events, and AEs (including AEs occurring within the first 30 minutes after each vaccination).

For tier 1 AEs, an unconditional exact method for deriving the 95% CI for the risk difference and p-value proposed by Chan and Zhang (1999) will be used to compare 13vPnC with Hib vaccine.

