For tier 2 AEs, the Miettinen and Nurminen method will be used to derive the 95% CI for the risk difference between 13vPnC and Hib vaccine.

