6.1.2. Primary Safety Endpoints

6.1.2.1. Primary Analysis

Endpoints: Safety endpoints in Section 3.1.

• Analysis time points:

Endpoints for Local reactions and systemic events: 7 days after each vaccination in Cohort 2, 3 and 4.

Endpoints for AEs and SAEs: from the signing of the ICD to 1 month after the last vaccination (13vPnC or Hib vaccine) in Cohort 2, 3 and 4.

Endpoints for SAEs: from the signing of the ICD to 6 month after the last vaccination (13vPnC or Hib vaccine) in Cohort 2, 3 and 4.

Endpoint for newly diagnosed chronic medical conditions: from 1 month after the last vaccination (13vPnC or Hib vaccine) in Cohort 2, 3, and 4 to 6 months after the last study vaccination in Cohort 2, 3, and 4.

- Analysis population: Safety population.
- Analysis methodology: Descriptive.
- Supporting objective: Primary Objective.

Reporting Results:

The number, proportion, and the corresponding 95% CI will be presented for each vaccine group in Cohort 2, 3 and 4.

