6.4.1. Adverse Events

It should be recognized that most studies are not designed to reliably demonstrate a causal relationship between the use of a pharmaceutical product and an AE or a group of AEs. Except for select events in unique situations, studies do not employ formal adjudication procedures for the purpose of event classification.

For tier 1 and tier 2 events, the proportion of AEs observed in each vaccine group will be presented along with the point estimates and associated 95% CIs of the risk difference (the difference of incidence rates) between 13vPnC and Hib vaccine in Cohort 2, 3, 4.

For tier 1 events, 95% CIs will be calculated using the exact methods proposed by Chan and Zhang described in Section 5.2.1.

For tier 2 events, 95% CIs will be calculated using the Miettinen and Nurminen method described in Section 5.2.1.

For tier 1 events, p-values from Chan and Zhang's method will be calculated and included in the presentations. AEs will be arranged in the output sorted in descending order of point estimates of the risk difference (the difference of incidence rates) within system organ class.

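### Cohorts 2 and 3: the stated AE window ends at least 56 days later for 13vPnC than for Hib (study doses only), other text points to a shared follow-up visit, and the tier 1/2 risk differences do not say which applies

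*SAP*

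**What the plan says.** **The window.** SAP 3.1.2 counts "The incidence of AEs from the signing of the informed consent document (ICD) to 1 month after the last vaccination (13vPnC or Hib" in Cohorts 2, 3 and 4. SAP 6.1.2.1 repeats the anchor: "from the signing of the ICD to 1 month after the last vaccination (13vPnC or Hib vaccine". Protocol 8.1.4 ends active AE collection at the same point: "until 1 month after the last vaccination (13vPnC or Hib". In SAP 3.1.2 the SAE and chronic-condition bullets count from the last *study* vaccination; the AE bullet omits that word.

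**The schedules.** Under protocol Table 5 (SAP Table 2), Hib recipients receive no study dose at Cohort 2 Visit 3 or Cohort 3 Visit 2. 13vPnC recipients are dosed at those visits, at least 56 days after their previous dose. Cohort 4 has one dose in each arm.

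**The contrasts.** SAP 6.4.1 plans "associated 95% CIs of the risk difference (the difference of incidence rates) between 13vPnC and Hib vaccine in Cohort 2, 3, 4" for tier 1 and tier 2 events. The methods are in SAP 5.2.1: "For tier 1 AEs, an unconditional exact method for deriving the 95% CI for the risk difference and p-value" (Chan-Zhang), and for tier 2 "the Miettinen and Nurminen method will be used to derive the 95% CI for the risk difference between 13vPnC and Hib vaccine". Under SAP 3.4.1 a preferred term outside tier 1 "is defined as a tier-2 event if there are at least 5% in any vaccine group". The readable text of these sections names no observation window and no adjustment for exposure time. Part of SAP 3.4.1 is redacted.

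**The visits.** Protocol 6.2.3, 6.2.4, 6.3.2 and 6.3.3 record AEs since the last visit in all subjects, up to Cohort 2 Visit 4 and Cohort 3 Visit 3. Tables 2 and 3 mark AE collection there without restricting it to one arm.

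**The concern.** A proportion with an event grows with the time observed. If each arm stops 1 month after its own last study dose, a background illness with the same rate in both arms has more days to appear under 13vPnC. The risk difference then leans against 13vPnC without any vaccine effect, and preferred terms reach the 5% rule mainly through the 13vPnC arm.

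Protocol 1.2 gives the Hib arm the role of safety control, and these contrasts are how the SAP compares AEs with that control. Two programmers following the text could produce different tables. A site following 8.1.4 could stop collecting Hib AEs before visits at which the procedures still ask for them.

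**Working it through.** **Step 1. Reproduce the plan's own figures.**
- Group size: 150/(1 − 0.15) = 176.5, rounded up to 177; at 2:1 this is 118 and 59, as in protocol Table 15.
- Cohort 3 participation is given as about 8 months (protocol 3.2). On the 13vPnC schedule, 56 + 168 = 224 to 56 + 196 = 252 days; divided by 30.44 this is 7.4 to 8.3 months, which agrees. Counted from the single Hib dose, 168 to 196 days is 5.5 to 6.4 months, which does not.
- Cohort 2 maximum: 449 − 210 + 196 = 435 days, or 14.3 months, against a stated 14 or so.

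**Step 2. Window length from Visit 1 on the stated wording, study doses only.** One month is taken as 28 or 42 days, the limits of the follow-up visit window.
- Cohort 3, minimum gap: 56 + 28 = 84 versus 28 days (3.0-fold), or 56 + 42 = 98 versus 42 days (2.3-fold). The protocol sets no maximum gap.
- Cohort 2, minimum gaps: 28 + 56 + 28 = 112 versus 28 + 28 = 56 days (2.0-fold).
- Cohort 2, all permitted dates: the lowest ratio is at Visit 1/2/3 ages of 210/393/449 days with 42 days, (449 − 210 + 42)/(393 − 210 + 42) = 281/225 = 1.25. The highest is at 210/238/449 with 28 days, (449 − 210 + 28)/(238 − 210 + 28) = 267/56 = 4.8.
- Ending both arms at the shared visit makes the ratio about 1.0.

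**Step 3. Effect on the contrasts when there is no vaccine effect.** The documents give no AE rates, so the rates are assumptions. With a constant rate p per 30 days, the risk over d days is 1 − (1 − p)^(d/30). At p = 5%, for example, 84 days gives 1 − 0.95^2.8 = 13.4% and 28 days gives 1 − 0.95^0.933 = 4.7%, an apparent excess of 8.7 points. The table sums the exact binomial probabilities (118 versus 59) of all outcomes whose 95% lower limit for 13vPnC minus Hib lies above 0.

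| Method, days 13vPnC vs Hib | 1% | 2% | 5% | 10% |
|---|---|---|---|---|
| Miettinen-Nurminen, Cohort 3, 84 vs 28 | 1.0% | 11.8% | 45.2% | 76.2% |
| Miettinen-Nurminen, Cohort 3, 98 vs 42 | 2% | 12% | 37% | 65% |
| Miettinen-Nurminen, Cohort 2, 112 vs 56 | 2% | 11% | 31% | 55% |
| Chan-Zhang, Cohort 3, 84 vs 28 | 0.1% | 4% | 32% | 68% |
| Miettinen-Nurminen, common 84 vs 84 | 0.3% | 1.6% | 2.3% | 2.4% |

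With the common 84-day window the Chan-Zhang figure is at most 1.4%.

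**Step 4. The 5% rule at 2% per 30 days.** Reaching 5% needs 6 of 118 or 3 of 59. With 84 versus 28 days, 64% of terms reach it in the 13vPnC arm and 10% in the Hib arm. With 84 days in both arms it is 64% and 64%.

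**The case against.** The strongest reply is that the shared visit is what the authors meant. Much of the text supports this:
- AE recording at Cohort 2 Visit 4 and Cohort 3 Visit 3 covers both arms, although neighbouring diary items are limited to 13vPnC recipients.
- Protocol 7.5.2 and SAP 3.2.1 describe Hib samples as taken 1 month after the last vaccination or dose, and protocol 7.4 places those draws at these same visits.
- The single Cohort 3 duration fits only the 13vPnC schedule.

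This stands as far as it goes, and on that reading there is no bias. But three places state the other window, 8.1.4 contradicts the visit procedures for Hib recipients, and nothing settles which governs the contrasts.

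The 56-day minimum also depends on counting study doses only. Cohort 2 Hib recipients are offered further Hib vaccination outside the study (protocol 5.6.3). If such a dose counts as the last vaccination, the gap could be shorter. This objection stands for Cohort 2.

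SAP 6.4 asks for safety summaries by dose, which would compare like with like for doses given in both arms. It defines no AE window, however, and its split into infant series and toddler dose does not fit Cohort 3. The redacted part of SAP 3.4.1 may state a window, so one cannot be said to be absent from the plan.

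Finally, the contrasts are descriptive. SAP 5.1 says: "There are also no formal statistical decision rules for this study and a descriptive estimation approach will be used". That is conceded: no success criterion depends on them, although tier 1 events do get p-values.

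A reader might infer that the trial's AE comparison is biased, or that the primary safety results are. The documents support neither. The first holds only on one of two open readings. The primary AE summaries are given per arm, without a contrast.

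**Conclusion.** This is a real but minor inconsistency. The only AE window stated in words gives unequal observation in Cohorts 2 and 3. The procedures point to equal observation, and the readable text does not assign either to the tier 1/2 risk differences or the 5% rule.

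The size depends on three assumptions: the stated window is applied to the contrasts, only study doses count, and background rates are constant and equal in the two arms. Under these, the false-excess probability in Cohort 3 at the minimum gap runs from about 1% for an event at 1% per 30 days to about 76% at 10% per 30 days. The upper end needs a single event affecting about 26% of children over 84 days (1 − 0.90^2.8). For rare events the effect is negligible.

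The per-arm primary summaries, 7-day reactogenicity and Cohort 4 are unaffected.

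**What to change.** 1. In SAP 5.2.1 and 6.4.1, and for the 5% rule, use one common interval in both arms: from consent to the shared 1-month follow-up visit (Cohort 2 Visit 4, Cohort 3 Visit 3, Cohort 4 Visit 2). Add a dose-matched window, 1 month after each dose given in both arms, as a fixed supporting analysis. Do not choose between them according to how complete the data look.
2. Reconcile protocol 8.1.4 with 6.2.3, 6.2.4, 6.3.2 and 6.3.3 on when AE collection ends for Hib recipients, and state whether the last vaccination means the last study vaccination.
3. Show follow-up days per arm beside the AE and SAE proportions. The 6-month contact is also timed from the last study vaccination, so it is not a shared date either.
4. SAP section 2 says the analyses have already been run for the primary report, so label the changed contrasts in the supplemental report as added after it.

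The cost is SAP wording, a window flag, one more set of AE tables and a protocol clarification; no data are added and no primary endpoint is redefined. The downside is that non-study Hib doses fall inside the common interval, so it compares schedules rather than single doses. The dose-matched window is less precise and cannot see events after the additional 13vPnC dose.

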3.2. Secondary Endpoint(s)

For OPA-related immunogenicity endpoints below, a random subset of approximately 50 subjects randomized to receive 13vPnC for each cohort (Cohort 1, 2, 3, 4) will be selected for OPA testing, and a random subset of approximately 25 subjects randomized to receive Hib vaccine for each cohort (Cohort 2, Cohort 3, Cohort 4) will be selected for OPA testing. Those random subsets will be performed by randomly ordering all subjects with adequate serum volume and selecting enough subjects (probably more than 50) assigned to receive 13vPnC in each cohort and enough subjects (probably more than 25) assigned to receive Hib vaccine in Cohort 2, 3, 4 to provide around 50 results for each serotype in 13vPnC at each planned blood draw visit for each cohort, and around 25 results for each serotype in Hib vaccine at each planned blood draw visit for each Cohort 2, 3 and 4.

3.2.1. Secondary Immunogenicity Endpoints

- The serotype-specific OPA geometric mean titers (GMTs) for each of the pneumococcal serotypes measured in a subset of approximately 50 subjects per cohort measured 1 month after the last dose of 13vPnC in Cohort 2, 3, 4 compared to OPA GMTs measured 1 month after the infant series in Cohort 1.
- Serotype-specific IgG GMCs in all subjects and OPA GMTs in approximately 50 subjects per cohort vaccinated with 13vPnC (Cohort 2, 3, 4) and approximately 25 subjects per cohort vaccinated with Hib (Cohort 2, 3, 4) using blood drawn at the following visits:
 - o Cohort 2: Visit 1, Visit 4
 - Cohort 3: Visit 1, Visit 3
 - Cohort 4: Visit 1, Visit 2
- Serotype-specific IgG GMCs in all subjects and OPA GMTs in approximately 50 subjects at all times points in Cohort 1.
- Proportion of subjects achieving a serotype-specific IgG concentration ≥0.35 µg/mL for each of the pneumococcal serotypes measured 1 month after the last dose in all subjects per cohort vaccinated with 13vPnC (Cohort 2,3, 4) and all subjects per cohort vaccinated with Hib (Cohort 2, 3, 4), and 1 month after the infant series in all subjects vaccinated with 13vPnC in Cohort 1.
- Proportion of subjects achieving a serotype-specific OPA titer ≥ the lower limit of quantitation (LLOQ) for each of the pneumococcal serotypes measured 1 month after the last dose in approximately 50 subjects per cohort vaccinated with 13vPnC (Cohort 2, 3, 4) and approximately 25 subjects per cohort vaccinated with Hib (Cohort 2, 3, 4) and

1 month after the infant series in approximately 50 subjects vaccinated with 13vPnC in Cohort 1.

3.2.2. Secondary Safety Endpoints

- The incidence of AEs from the signing of the ICD to 1 month after vaccination 3 in Cohort 1.
- The incidence of newly diagnosed chronic medical conditions from 1 month after vaccination 3 to vaccination 4 in Cohort 1.
- The incidence of AEs from vaccination 4 to 1 month after vaccination 4 in Cohort 1.
- The incidence of newly diagnosed chronic medical conditions from 1 month after vaccination 4 to 6 months after vaccination 4 in Cohort 1.
- The incidence of SAEs from the signing of the ICD to 6 months after vaccination 4 in Cohort 1.

3.3. Other Endpoints

Not applicable.

3.4. Safety Endpoints

3.4.1. Adverse Events

CCI

Tier-1 events: These are pre-specified events of clinical importance and are maintained in a list in the product's Safety Review Plan.

Tier-2 events: These are events that are not tier-1 but are "common". A Medical Dictionary for Regulatory Activities (MedDRA) preferred term (PT) is defined as a tier-2 event if there are at least 5% in any vaccine group.

CCL

3.4.2. Reactogenicity Endpoints

Reactogenicity data captured in the electronic diary (e-diary) for Cohorts 2, 3, and 4 after each investigational product (13vPnC or Hib vaccine) vaccination consist of local reactions (redness, swelling, and tenderness), systemic events (fever, decreased appetite, drowsiness, irritability, fatigue, headache, vomiting, diarrhea, muscle pain, joint pain) and use of antipyretic medication to prevent or treat symptoms.

